Injection Site Pain (pain without touching) Or Tenderness (pain when area is touched)	Pain/tenderness causing no or minimal limitation of use of limb	Pain/tenderness limiting use of limb OR Pain/tenderness causing greater than minimal interference with usual social & functional activities	Pain/tenderness causing inability to perform usual social & functional activities	Pain/tenderness causing inability to perform basic self-care function OR Hospitalization (other than ER visit) indicated for management of pain/tenderness
Injection Site Reaction (Localized), > 15 Years Pediatric ≤ 15 Years	Erythema OR Induration of 5 × 5 cm to 9 × 9 cm (or 25–81 × cm ²) Erythema OR Induration OR Edema present but ≤ 2.5 cm diameter	Erythema OR Induration OR Edema > 9 cm any diameter (or > 81 cm ²) Erythema OR Induration OR Edema > 2.5 cm diameter but < 50% surface area of the extremity segment (eg, upper arm/thigh)	Ulceration OR Secondary infection OR Phlebitis OR Sterile abscess OR Drainage Erythema OR Induration OR Edema involving ≥ 50% surface area of the extremity segment (eg, upper arm/thigh) OR Ulceration OR Secondary infection OR Phlebitis OR Sterile abscess OR Drainage	Necrosis (involving dermis and deeper tissue) Necrosis (involving dermis and deeper tissue)
Pruritis Associated with Injection See also Skin: Pruritis (itching—no skin lesions)	Itching localized to injection site AND Relieved spontaneously or with < 48 h treatment	Itching beyond the injection site but not generalized OR Itching localized to injection site requiring ≥ 48 h treatment	Generalized itching causing inability to perform usual social & functional activities	NA

ENDOCRINE/METABOLIC				
	Grade 1	Grade 2	Grade 3	Grade 4
Lipodystrophy (eg, back of neck, breasts, abdomen)	Detectable by study participant or caregiver (for young children and disabled adults)	Detectable on physical exam by health care provider	Disfiguring OR Obvious changes on casual visual inspection	NA
Diabetes Mellitus	NA	New onset without need to initiate medication OR Modification of current meds to regain glucose control	New onset with initiation of indicated med OR Diabetes uncontrolled despite treatment modification	Life-threatening consequences (eg, ketoacidosis, hyperosmolar non-ketotic coma)
Gynecomastia	Detectable by study participant or caregiver (for young children and disabled adults)	Detectable on physical exam by health care provider	Disfiguring OR Obvious on casual visual inspection	NA
Hyperthyroidism	Asymptomatic	Symptomatic causing greater than minimal interference with usual social & functional activities OR Thyroid suppression therapy indicated	Symptoms causing inability to perform usual social & functional activities OR Uncontrolled despite treatment modification	Life-threatening consequences (eg, thyroid storm)
Hypothyroidism	Asymptomatic	Symptomatic causing greater than minimal interference with usual social & functional activities OR Thyroid replacement therapy indicated	Symptoms causing inability to perform usual social & functional activities OR Uncontrolled despite treatment modification	Life-threatening consequences (eg, myxedema coma)
Lipoatrophy (eg, fat loss from the face, extremities, buttocks)	Detectable by study participant or caregiver (for young children and disabled adults)	Detectable on physical exam by health care provider	Disfiguring OR Obvious on casual visual inspection	NA

GENITOURINARY				
	Grade 1	Grade 2	Grade 3	Grade 4
Intermenstrual Bleeding (IMB)	Spotting observed by participant OR Minimal blood observed during clinical or colposcopic exam	Intermenstrual bleeding not greater in duration or amount than usual menstrual cycle	Intermenstrual bleeding greater in duration or amount than usual menstrual cycle	Hemorrhage with life-threatening hypotension OR Operative intervention indicated
Urinary Tract obstruction (eg, stone)	NA	Signs or symptoms of urinary tract obstruction without hydronephrosis or renal dysfunction	Signs or symptoms of urinary tract obstruction with hydronephrosis or renal dysfunction	Obstruction causing life-threatening consequences

INFECTION				
	Grade 1	Grade 2	Grade 3	Grade 4
Infection (any other than HIV infection)	Localized, no systemic anti-infective treatment indicated AND Symptoms causing no or minimal interference with usual social & functional activities	Systemic anti-infective treatment indicated OR Symptoms causing greater than minimal interference with usual social & functional activities	Systemic anti-infective treatment indicated AND Symptoms causing inability to perform usual social & functional activities OR Operative intervention (other than simple incision and drainage) indicated	Life-threatening consequences (eg, septic shock)

Basic Self-care Functions: Activities such as bathing, dressing, toileting, transfer/movement, continence, and feeding.

Usual Social & Functional Activities: Adaptive tasks and desirable activities, such as going to work, shopping, cooking, use of transportation, pursuing a hobby, etc.

Appendix 5. Child -Pugh-Turcotte Score

Child-Pugh classification of severity of liver disease

Parameter	Points assigned		
	1	2	3
Ascites	Absent	Slight	Moderate
Bilirubin	<2 mg/dL (<34.2 micromol/liter)	2-3 mg/dL (34.2 to 51.3 micromol/liter)	>3 mg/dL (>51.3 micromol/liter)
Albumin	>3.5 g/dL (35 g/liter)	2.8-3.5 g/dL (28 to 35 g/liter)	<2.8 g/dL (<28 g/liter)
Prothrombin time			
Seconds over control	<4	4-6	>6
INR	<1.7	1.7-2.3	>2.3
Encephalopathy	None	Grade 1-2	Grade 3-4

Modified Child-Pugh classification of the severity of liver disease according to the degree of ascites, the plasma concentrations of bilirubin and albumin, the prothrombin time, and the degree of encephalopathy. A total score of 5-6 is considered grade A (well-compensated disease); 7-9 is grade B (significant functional compromise); and 10-15 is grade C (decompensated disease). These grades correlate with one- and two-year patient survival: grade A - 100 and 85 percent; grade B - 80 and 60 percent; and grade C - 45 and 35 percent.

## LIST OF ABBREVIATIONS

AE	adverse event
ALT	alanine aminotransferase
ANOVA	analysis of variance
AST	aspartate aminotransferase
AUC	area under the curve
BID	twice daily
BLQ	below limit of quantitation
BMI	body mass index
BUN	blood urea nitrogen
CV	coefficient of variation
CI	confidence interval
CBC	complete blood cell count
C max	maximum concentration
CPT	Child-Pugh-Turcotte
CRF	case report form(s)
CSR	clinical study report
DOB	date of birth
ECG	electrocardiogram
eCRF	electronic case report form(s)
eGFR	Estimated glomerular filtration rate
ENTO	entospletinib
ET	early termination
GLSM	geometric least squares mean
HBV	hepatitis B virus
HCV	hepatitis C virus
HDL	high-density lipoprotein
HLT	high-level term
HIV	human immunodeficiency virus
INR	International Normalized Ratio
LDL	Low-density lipoprotein
LLOQ	lower limit of quantitation
MedDRA	Medical Dictionary for Regulatory Activities
PK	Pharmacokinetic(s)
PT	preferred term
Q1	first quartile
Q3	third quartile
QD	once daily
SAE	serious adverse event
SAP	statistical analysis plan
SD	standard deviation

SOC	system organ class
TFL	tables, figures, and listings
THC	tetrahydrocannabinol
ULN	upper limit of the normal range
ULOQ	upper limit of quantification
WHO	World Health Organization

## 1. INTRODUCTION

This statistical analysis plan (SAP) describes the statistical analysis methods and data presentations to be used in tables, figures, and listings (TFLs) in the clinical study report (CSR) for Study GS-US-339-1631. This SAP is based on the study protocol amendment 4 dated 30 November 2016 and the electronic case report form (eCRF). The SAP will be finalized prior to database finalization. Any changes made after finalization of the SAP will be documented in the CSR.

### 1.1. Study Objectives

The primary objective of this study is as follows:

- To evaluate the pharmacokinetics (PK) of Entospletinib (ENTO) and/or its metabolites (if applicable) in subjects with impaired hepatic function (stratified by smoking status, as appropriate) relative to matched, healthy controls

The secondary objectives of this study are as follows:

- To evaluate the safety and tolerability of administration of ENTO in subjects with normal and impaired hepatic function,
- To evaluate the potential impact of smoking on the PK of ENTO in subjects with moderate hepatic impairment.

### 1.2. Study Endpoint

The primary endpoints are the PK parameters area under the curve (AUC) and maximum concentration ( $C_{max}$ ) of ENTO and/or its metabolites (if applicable). The secondary endpoints are the incidences of adverse events and laboratory abnormalities.

### 1.3. Study Design

This is an open-label, parallel-group, adaptive, multiple-dose, Phase 1 study evaluating the PK of ENTO and/or its metabolites (if applicable) in subjects with impaired hepatic function relative to matched, healthy control subjects.

This study will enroll a minimum of 40 and a maximum of 80 subjects using an adaptive study design that includes up to 3 enrolled cohorts of subjects with hepatic impairment as well as matched healthy controls. Eligible subjects will be male and nonpregnant, nonlactating female subjects, aged  $\geq 18$  years,  $18 \leq \text{BMI} \leq 40$ , with either impaired hepatic function of Child-Pugh-Turcotte (CPT) classification A, B, or C or with normal hepatic function. Each subject in the control group will be matched to a subject with impaired hepatic function by age ( $\pm 10$  years), gender, and BMI ( $\pm 20\%$ ).

Based on safety and/or PK results from subjects with moderate hepatic impairment (Cohort 1), subjects with severe hepatic impairment (Cohort 2) and/or mild hepatic impairment (Cohort 3) will be enrolled as follows:

### **Cohort 1 (Moderate Hepatic Impairment) Initial Cohort**

Up to 40 subjects: 20 with moderate hepatic impairment (10 smokers [at least 8 evaluable] and 10 non-smokers [at least 8 evaluable]), 20 matched healthy controls (at least 8 evaluable healthy controls matched to smokers with moderate impairment, and at least 8 evaluable healthy controls matched to non-smokers with moderate hepatic impairment).

### **Adaptive Cohort 2 (Severe Hepatic Impairment)**

Up to 20 subjects: 10 with severe impairment, up to 10 matched healthy controls, for 8 evaluable subjects per group. Data from healthy subjects in Cohort 1 who are an appropriate match for a severe hepatic impairment subject may be used.

### **Adaptive Cohort 3 (Mild Hepatic Impairment)**

Up to 20 subjects: 10 with mild impairment, up to 10 matched healthy controls, for 8 evaluable subjects per group. Data from healthy subjects in Cohort 1 or 2 who are an appropriate match for a mild impairment subject may be used.

[figure not shown]
Cohort 1 enrollment of hepatic impairment subjects will be an approximate even distribution of subjects who are active cigarette smokers (at least 10 cigarettes/day) and subjects who are current non-smokers (no use of tobacco, nicotine-containing or tetrahydrocannabinol (THC)-containing products within the last 14 days). Hepatic impairment subjects enrolled in adaptive Cohorts 2 and 3 will be current non-smokers (no use of tobacco, nicotine-containing or THC-containing products within the last 14 days).

Designations of hepatic impairment will be assigned as follows:

- Class A (mild): CPT score 5 to 6
- Class B (moderate): CPT score 7-9
- Class C (severe): CPT score 10-15

[figure not shown]
An overview of the study design is shown below in [Figure 1-1](#).

**Figure 1-1. Study Design**

The study schema for all subjects is shown in [Figure 1-2](#).

**Figure 1-2. Study Schema – All Cohorts**

#### **1.4. Sample Size and Power**

Eight evaluable subjects per hepatic function group (for Cohort 1, it is 8 evaluable subjects per hepatic function group within each smoking status group) will provide  $\geq 89\%$  probability for the 90% confidence interval (CI) for the geometric least-squares mean (GLSM) ratio of PK parameters (AUC or  $C_{\max}$ ) for ENTO in the hepatic impairment/dysfunction group(s) versus the appropriate group of matched, healthy controls, to be within limits of 50% to 200%. The calculation assumes an expected ratio of geometric least-squares means of 1.0 in PK parameters and inter-subject standard deviation of 0.455 for the natural logarithm-transformed pharmacokinetic parameters for ENTO. The assumption is based on the data obtained from a prior clinical study of ENTO (Study GS-US-339-0111).

## **2. PLANNED ANALYSES**

### **2.1. Primary Analysis**

The primary analysis objective of this study is to evaluate the multiple-dose PK of ENTO and/or its metabolites (if applicable) in subjects with normal hepatic function, mild hepatic impairment, moderate hepatic impairment, and severe hepatic impairment.

The primary endpoints are the PK parameters AUC and  $C_{\max}$  of ENTO and/or its metabolites (if applicable).

A parametric (normal theory) analysis of variance (ANOVA) using a linear model will be fitted to the natural logarithmic transformation of PK parameters ( $AUC_{\tau}$  and  $C_{\max}$ ) for ENTO and/or its metabolites. The 90% confidence intervals (CIs) will be constructed for the GLSM ratios of each of the PK parameters in the hepatic impairment group versus the normal liver function group (see Section 5.2.2).

### **2.2. Secondary Analysis**

The secondary analysis of this study will evaluate the safety and tolerability of ENTO in subjects with normal and impaired hepatic function using the incidence and severity of treatment-emergent adverse events and laboratory abnormalities (see Section 6).

### **2.3. Changes from Protocol-Specified Analysis**

No changes from protocol-specified analyses are planned.

### **3. GENERAL CONSIDERATIONS FOR DATA ANALYSIS**

#### **3.1. Analysis Considerations**

Analysis results will be presented using descriptive statistics. For categorical variables, the number and percentage of subjects in each category will be presented; for continuous variables, the number of subjects (n), mean, standard deviation (SD) or standard error (SE), median, first quartile (Q1), third quartile (Q3), minimum, and maximum will be presented.

By-subject listings will be presented for all subjects in the All Enrolled Analysis Set, and sorted by subject identification (ID) number in ascending order, visit date, and time (if applicable), unless otherwise specified. Data collected on log forms, such as AEs, will be presented in chronological order within subject. The treatment group to which subjects were initially assigned will be used in the listings. Age, sex at birth, race, and ethnicity will be included in the listings, as space permits.

#### **3.2. Analysis Sets**

Analysis sets define which subjects are included in different analyses.

##### **3.2.1. All Enrolled Analysis Set**

The all enrolled analysis set will include subjects who were enrolled into the study.

This is the primary analysis set for all listings.

##### **3.2.2. Safety Analysis Set**

The safety analysis set will include all randomized subjects who received at least one dose of study drug.

This is the primary analysis set for safety summary tables.

##### **3.2.3. Pharmacokinetic (PK) Analysis Set**

The PK analysis sets for ENTO and/or its metabolites will include all enrolled subjects who received at least one dose of ENTO and had at least one evaluable PK concentration data value reported by the PK lab, for each analyte respectively.

This is the primary analysis set for PK summary tables and figures.

#### **3.3. Strata and Covariates**

Each subject in the control group will be matched to a subject with impaired hepatic function by age ( $\pm 10$  years: age  $\geq 18$ ), sex, and body mass index ( $\pm 20\%$ :  $18 \leq \text{BMI} \leq 40$ ).

### **3.4. Examination of Subject Subsets**

Some baseline variables (i.e., body weight, height, and BMI) will be summarized for males and females separately.

### **3.5. Multiple Comparisons**

All endpoint tests will be done at the significance level of 0.05 with no multiplicity adjustments made for testing.

### **3.6. Missing Data and Outliers**

In general, values will not be imputed for missing laboratory and vital signs data. If the subject is missing a predose value, then the subject will be excluded from the calculation of summary statistics for the predose value and all change from predose values. Similarly, if the subject is missing a postdose value, then the subject will be excluded from the calculation of summary statistics for that postdose and change from predose value (see Section 3.8.2 and Section 3.8.3 for more details).

Missing values will not be imputed for categorical data, such as safety electrocardiogram (ECG).

### **3.7. Data Handling Conventions and Transformations**

In general, age (in years) on the date of the first dose of study drug will be used for analyses and presentation in listings. If an enrolled subject was not dosed with any study drug, the enrollment date will be used instead of the first dosing date of study drug. If only the birth year is collected on the CRF, “01 July” will be used for the unknown birth day and month for the purpose of age calculation. If only birth year and month are collected, “01” will be used for the unknown birth day.

Pharmacokinetic concentration values that are below the limit of quantification (BLQ) will be presented as “BLQ” in the concentration data listing. Values that are BLQ will be treated as zero at predose and one-half the value of the lower limit of quantitation (LLOQ) at postdose timepoints for determination of summary and order statistics.

For the presentation of summary and order statistics, if at least one subject has a concentration value of BLQ for the timepoint, then the minimum value will be displayed as “BLQ.” If more than 25% of subjects have a concentration data value of BLQ for a given timepoint, then the minimum and first quartile (Q1) will be displayed as “BLQ.” If more than 50% of the subjects have a concentration data value BLQ for the timepoint, then the minimum, Q1, and median values will be displayed as “BLQ”. If more than 75% of the subjects have a concentration data value of BLQ for a given timepoint, then the minimum, Q1, median, and third quartile (Q3) values will be displayed as “BLQ”. If all subjects have concentration data values BLQ for the timepoint, then all summary and order statistics will be displayed as “BLQ”. (See Section 5.2.1 for details on the presentation of summary statistics for PK concentration values.)

Exposure parameters selected for statistical analysis will be natural-log transformed (see Section 5.2.2). PK parameter values that are BLQ will be presented as “BLQ” in the parameter data listing. For the purpose of calculation, PK concentration values below the limit of quantitation will be assigned a value of zero for predose and imputed to half of the LLOQ for postdose in determining summary and order statistics.

Laboratory data that are continuous in nature but are less than the LLOQ or above the upper limit of quantitation (ULOQ) will be imputed to the value of the lower or upper limit plus or minus 1 significant digit, respectively (e.g., if the results of a continuous laboratory test is < 20 or 2.0, a value of 19 or 1.9, respectively, will be used in computing summary statistics). An exception to this rule is any value reported as < 1 or <0.1, etc. For values reported as < 1 or < 0.1, a value of 0.9 or 0.09, respectively, will be used to calculate summary statistics.

The limit of quantification will be used for calculation of descriptive statistics if the datum is reported in the form of “<= x” or “>= x”, where x is considered the limit of quantification.

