8.3. Data Handling Conventions

For summary statistics, PK concentration values below the limit of quantitation (BLQ) will be treated as zero at predose and one-half of the lower limit of quantitation (LLOQ) for postdose timepoints, where LLOQ is corrected for the dilution factor (ie, reported dilution/dilution factor).

Laboratory data that are continuous in nature but are less than the lower limit of quantitation or above the upper limit of quantitation will be imputed to the value of the lower or upper limit minus or plus one significant digit, respectively (eg, if the result of a continuous laboratory test is < 20, a value of 19 will be assigned; if the result of a continuous laboratory test is < 20.0, a value of 19.9 will be assigned).

Missing data can have an impact upon the interpretation of the trial data. As this study is of short duration, it is anticipated that missing data will be minimal. In general, values for missing data will not be imputed. However, a missing pretreatment laboratory result would be treated as normal (ie., no toxicity grade) for the laboratory abnormality summary.

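### SAP 3.7 swaps the signs in the laboratory imputation rule relative to protocol 8.3 and its own examples, which leaves values above the ULOQ with only a wrong-way instruction

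*SAP*

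**What the plan says.** SAP 3.7 sets a rule for continuous laboratory results outside the assay's quantitation range. It names two cases in order, results under the LLOQ and then results over the ULOQ, and says that they are "imputed to the value of the lower or upper limit plus or minus 1 significant digit, respectively". The same sentence gives an example for use in the summaries, of which the main part is "if the results of a continuous laboratory test is < 20 or 2.0, a value of 19 or 1.9, respectively, will be used in computing". For very small limits the SAP makes an exception: "For values reported as < 1 or < 0.1, a value of 0.9 or 0.09, respectively, will be used to calculate summary statistics". The next paragraph of SAP 3.7 says that a result reported as <= x or >= x takes x itself.

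Protocol 8.3 has the same rule with the sign words in the other order: "imputed to the value of the lower or upper limit minus or plus one significant digit, respectively". Its example agrees with that order: "if the result of a continuous laboratory test is < 20, a value of 19 will be assigned". It also takes < 20.0 to 19.9.

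SAP 2.3 states "No changes from protocol-specified analyses are planned", and SAP 1 says that the SAP is based on protocol amendment 4.

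**The concern.** The word at the end of the SAP rule pairs the signs with the limits one for one, so the rule cannot be read as a loose plus-or-minus. It says lower limit plus, upper limit minus. That is the reverse of the protocol, and it does not agree with the figures printed beside it.

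The two limits are not equally exposed. Below the LLOQ, a programmer has worked values to follow. Above the ULOQ the SAP has no worked value, and the transposed phrase is its only instruction. Coded as written, a result known to exceed the assay limit would enter the summaries as a value within it. SAP 6.2.2 sends such values into the predose, postdose and change-from-predose tables by hepatic function group.

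**Working it through.** **Inputs.** The sign order comes from SAP 3.7 and protocol 8.3, and the printed examples from the same sections. Neither document gives a ULOQ for any laboratory test, so the upper-limit figures use an assumed limit of 500, with 50.0 as a second case.

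**Formulas.** Let L be the limit and u one unit in its last reported digit.
- SAP as worded: below the LLOQ, L + u; above the ULOQ, L − u.
- Protocol 8.3: below the LLOQ, L − u; above the ULOQ, L + u.

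**Step 1: reproduce the printed examples, then extend to the upper limit.**

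| Result | u | SAP as worded | Protocol rule | Printed value |
|---|---|---|---|---|
| < 20 | 1 | 20 + 1 = 21 | 20 − 1 = 19 | 19 (SAP and protocol) |
| < 2.0 | 0.1 | 2.0 + 0.1 = 2.1 | 2.0 − 0.1 = 1.9 | 1.9 (SAP) |
| < 20.0 | 0.1 | 20.0 + 0.1 = 20.1 | 20.0 − 0.1 = 19.9 | 19.9 (protocol) |
| > 500 (assumed) | 1 | 500 − 1 = 499 | 500 + 1 = 501 | none |
| > 50.0 (assumed) | 0.1 | 50.0 − 0.1 = 49.9 | 50.0 + 0.1 = 50.1 | none |

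The SAP's wording does not reproduce its own examples; the protocol's wording reproduces all three. The SAP exception also goes downward, by a tenth of a unit: 1 − 0.1 = 0.9 and 0.1 − 0.01 = 0.09. Every printed value for a result below the limit therefore lies below the limit.

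**Step 2: size per value.** The two rules differ by (L + u) − (L − u) = 2u, that is 2 at a limit of 500 and 0.2 at 50.0.

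**Step 3: order against the neighbouring rule.** At the assumed limit of 500, >= 500 takes 500. The SAP wording gives > 500 the value 499, so the strictly higher report ranks lower. The protocol's 501 keeps the order.

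**Step 4: change from predose.** Take a quantified predose value p and a postdose result > 500. The change is 499 − p under the SAP wording and 501 − p under the protocol.
- p = 500: −1 against +1, so the sign reverses.
- p = 499: 0 against +2.
- p below 499: positive under both rules, and still 2 apart.

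**Step 5: size in a group mean.** With k affected values among n subjects, the mean moves by 2uk/n. One affected value among 10 subjects, the planned number of impaired subjects in Cohort 2 or Cohort 3, moves it by 2/10 = 0.2 of a last-digit unit.

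**Step 6: which outputs are reached.** The SAP's example and exception refer to summary statistics. SAP 6.2.1 rules out inferential analysis of laboratory data. PK concentrations below the limit have their own rules (zero at predose and half the LLOQ postdose for summaries in SAP 3.7; a separate convention for parameter estimation in SAP 5.1), so AUC and Cmax are not touched. Laboratory abnormality incidence rests on the toxicity grades of SAP 6.2.3 to 6.2.5, and nothing in the documents shows a grade changing because of this rule.

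**The case against.** The strongest reply is that the text corrects itself. The SAP prints 19 for < 20 in the very sentence that holds the swapped signs, the SAP is built on the protocol, and SAP 2.3 can be taken as confirming that the protocol's rule is the intended one. A careful programmer would see the clash and ask. Each value moves by only two last-digit units, and the imputed value is a placeholder under either rule, so even the correct +1 says nothing about the true size of a rise.

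Most of this stands, and it limits the point in three ways where a reader might infer more.

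- **That results below the LLOQ will be set above it, such as 21 instead of 19.** The SAP's printed values contradict this. The figure of 21 arises only if the 19 given for exactly that case is ignored.
- **That impaired subjects will be affected more than controls.** Protocol 4.2.2 allows ALT and AST up to 10 × ULN at Screening in impaired subjects, while protocol 4.2.3 holds controls to 1 × ULN for these and for bilirubin and alkaline phosphatase. But the ULN is a reference limit, not an assay limit. Without a ULOQ, the documents cannot show that any result would be reported as above it, in either group.
- **That rises will commonly appear as falls.** Step 4 shows that this needs a predose value at the limit itself.

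The reply does not dispose of the upper limit. There the SAP offers no example to set against its wording, and the right answer can be found only by going back to protocol 8.3.

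**Conclusion.** The sign order in SAP 3.7 is transposed. It conflicts with protocol 8.3 and with the SAP's own examples, and it is not declared as a change. The lower-limit direction is settled by the printed values. What remains is that results above the ULOQ would, if coded from the SAP alone, be placed one last-digit unit inside the limit instead of one beyond it.

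This is a minor correction. It amounts to two last-digit units per affected value in descriptive laboratory and change-from-predose summaries, with no effect shown on PK results or toxicity grades. The sign conflict rests on the text alone. The upper-limit figures rest on an assumed ULOQ, and how often the rule would be used is unknown.

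**What to change.** In SAP 3.7, reverse the two sign words so that the phrase reads minus or plus 1 significant digit, as in protocol 8.3. Add one upper-limit example, such as a result of > 500 being summarised as 501, marked as illustrative. The existing lower-limit examples and the <= and >= convention can stay as they are.

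The cost is one wording change and one added example, with no effect on data collection or trial conduct. If the SAP is already final, record the correction in the CSR, as SAP 1 provides for later changes, and check that the laboratory summary programs use the protocol's direction at the upper limit.
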